7.1 Specification of Safety Parameters

As amitriptyline is known to cause cardiac conduction delays and lower the seizure threshold in some individuals, we will not enroll anyone with known cardiac disease or seizure history that would be allocated amitriptyline during the study. We will also not enroll anyone with bipolar disorder (to avoid causing mania) or medications that could interact with amitriptyline and cause serotonin syndrome that would be allocated amitriptyline during the study.

7.2 Methods and Timing for Assessing, Recording, and Analyzing Safety Parameters

Subjects will be instructed to call the research team if they have any questions or concerns during the study period. A research team member will call subjects approximately 1 week into the study period to confirm that they are taking their study medication as prescribed and to see if they have any questions or concerns. If so, a physician on the study team will reach out to them.

When subjects return for their follow-up visit, a study team member will inquire about any changes to their health or medical visits (including emergency room visits or hospitalizations) since their initial study visit. We will ask specifically if they experienced any adverse effects from the amitriptyline or omeprazole. If a subject reports a new or worsening symptom that is medically concerning (e.g., bright red blood per rectum), they will be referred for further evaluation.

7.3 Adverse Events and Serious Adverse Events

An **adverse event (AE)** is any unfavorable or unintended diagnosis, symptom, sign, syndrome or disease which either occurs during the study (having been absent at baseline), or if present at baseline, appears to worsen.

A **serious adverse event (SAE)** is any untoward medical occurrence that results in death, is life threatening, requires inpatient hospitalization or prolongation of existing hospitalization, results in persistent or significant disability/incapacity, or is a congenital anomaly.

During the follow-up visit, the study team member will specifically ask about any new or worsening symptoms in the last 8 weeks, unanticipated medical appointments, emergency room, or hospital visits.

In addition, during telephone check-ins, the study research coordinator will record any health concerns reported by subjects (not specifically solicited) and report these to the study PI. If there are any signs or symptoms of concern or that require further clarification, the study PI will contact the subject.

- Unexpected fatal or life-threatening AEs related to the intervention will be reported to the National Center for Complementary and Integrative Health (NCCIH) Program Officer within 3 business days of the investigator becoming aware of the event and to the study's Independent Safety Monitor(s) and UC Davis IRB within 5 business days of the investigator becoming aware of the event. Other serious and unexpected AEs related to the intervention will be reported within 5 business days.
- Anticipated or unrelated SAEs will be handled in a less urgent manner but will be reported to the Independent Safety Monitor(s), IRB, and other oversight organizations in accordance with their requirements and will be reported to NCCIH on an annual basis.
- All other AEs documented during the course of the trial will be reported to NCCIH and the UC Davis IRB on an annual basis by way of inclusion in the annual report and in the annual AE summary which will be provided to NCCIH and to the Independent Monitors. The Independent Safety Monitor(s) Report will state that all AEs have been reviewed (see Data Safety and Monitoring Plan).

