- Amitriptyline: The most common side effects are dry mouth, sleepiness, and constipation. Less common side effects include dizziness, fatigue, headache, agitation, tremor, blurred vision, nausea, insomnia, and sexual dysfunction. Rare side effects include an allergic reaction, changes in heart conduction causing slowing or speeding up of the heart rate, serotonin syndrome, and suicidal ideation. We are prescribing low doses of this medication and have excluded those most vulnerable to adverse effects and so do not anticipate any serious adverse events. If a study subject calls with concerns about side effects, they will be directed to speak with a physician on the study team to assess their symptoms and determine whether any dose modification or further evaluation is needed. If it is deemed that the subject should stop the medication, they will be instructed in how to do so. If it is determined that they need further medical evaluation, they will be instructed what to do.
- Omeprazole: The most common side effects are headaches, abdominal pain, diarrhea, and nausea. Less common side effects include skin rash, constipation, dizziness, and back pain. Rarely someone may develop a hypersensitivity reaction, acute interstitial nephritis, lupus, or an enteric infection. Long-term use may increase the risk of

fractures, vitamin B12 deficiency, or low magnesium levels. Despite these risks, omeprazole is generally well-tolerated and available over-the-counter. If a study subject calls with concerns about side effects, they will be directed to speak with a physician on the study team to assess their symptoms and determine whether any dose modification or further evaluation is needed. If it is deemed that the subject should stop the medication, they will be instructed in how to do so. If it is determined that they need further medical evaluation, they will be instructed what to do.

- Severe GERD symptoms: It is possible that subjects may experience a flare in their GERD symptoms during the study. If a subject calls with severe GERD symptoms, he or she will be directed to speak with a study physician to discuss their symptoms and determine the best course of action. In some cases as needed antacids may be recommended for refractory symptoms. If this recommendation does not suffice, the subject may need to initiate additional medication and possibly be removed from the study.

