9.4 Interim Analyses and Stopping Rules

No interim analyses are planned. The study PI will periodically review video recordings of visit interventions as the study progresses to offer feedback to the study intervention providers and ensure adherence to the protocol.

If at any point 20% or more of participants have dropped from the study due to adverse effects from amitriptyline or omeprazole and/or there is a serious adverse event likely due to amitriptyline or omeprazole, the study team will meet with the study safety monitor to determine whether any protocol modifications are necessary.

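### The Section 7.3 serious-event definition can leave a named drug reaction to the annual summary, and neither Section 7.3 nor 9.4 sets a time to the monitor for an anticipated drug-related SAE

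*Combined protocol and SAP*

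**What the plan says.** **Definition.** Under Section 7.3 an SAE "is any untoward medical occurrence that results in death, is life threatening, requires inpatient hospitalization or prolongation of existing hospitalization". The only other criteria are lasting disability and a birth defect.

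**Routes in Section 7.3.**
- "Unexpected fatal or life-threatening AEs related to the intervention will be reported to the National Center" (NCCIH, the funder) in 3 business days, and to the Independent Safety Monitor(s) and IRB in 5.
- Any other SAE that is both unexpected and related: 5 business days.
- "Anticipated or unrelated SAEs will be handled in a less urgent manner": to the monitor and IRB according to their own requirements, and to NCCIH once a year.
- Every other AE goes into the annual report and an annual AE summary, which the monitors receive.

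**Trigger in Section 9.4.** If 20% or more of participants have dropped from the study because of drug adverse effects, and/or "there is a serious adverse event likely due to amitriptyline or omeprazole, the study team will meet with the study safety monitor". The SAE limb has no expectedness condition, and the rule gives no time limit.

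**Named reactions.** Section 7 lists among the rare amitriptyline effects "changes in heart conduction causing slowing or speeding up of the heart rate, serotonin syndrome, and suicidal ideation", as well as allergic reaction. It also says that the team anticipates no serious events with amitriptyline at this dose in this population. For omeprazole it lists, among others, hypersensitivity and interstitial nephritis. Section 7.1 adds seizure and mania as reasons for exclusions from amitriptyline. Section 4.1 gives suicidality as a reason for the lower age limit.

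Section 7.6 refers to a separate monitoring plan in Appendix G, whose text was not available.

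**The concern.** The independent monitor is the one party outside the study team who can ask whether the protocol should change. The documents show which reactions matter most for amitriptyline, because exclusions and an age limit are built around them. Yet the SAE definition turns on outcome alone. Staff ask about emergency room visits (Sections 6.27, 7.2 and 7.3), but such a visit does not by itself make an event serious. A named reaction handled in the emergency room or as an outpatient can therefore stay within the study team for up to a year while enrolment continues.

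The second matter is a mismatch between sections. For one and the same event, an anticipated SAE likely due to study drug, Section 7.3 prescribes less urgency and Section 9.4 prescribes a meeting. Neither says by when the monitor must know.

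**Working it through.** The plan gives no figure on this point, so the main check sets the routes side by side. Two short calculations follow.

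**1. Routes to the monitor**

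| Event judged due to study drug | Class in 7.3 | Time to monitor in 7.3 | SAE limb of 9.4 |
|---|---|---|---|
| Fatal or life-threatening, unexpected | fast | 5 business days | met |
| Other SAE, unexpected | fast | 5 business days (recipients not restated) | met |
| Any SAE, anticipated | less urgent | no number of days | met, no time limit |
| Named reaction, not life-threatening, no admission or disability | other AE | annual summary | not met |

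The last row is the gap in the definition. The third row is the mismatch between sections.

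Two wording points blur the table. *Anticipated* and *unexpected* are not tied to any list: Section 7 lists the reactions as known effects but says no serious events are anticipated with amitriptyline, so an amitriptyline SAE could fall in row 2 or row 3. *Related to the intervention* could mean the randomized visit (Section 5.1) or the drug (listed in Section 5.3.2 as a required intervention).

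**2. Does the 20% limb of Section 9.4 act as a backstop?**

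The threshold is 0.20 × n: 2 of 10, 4 of 20, 6 of 30, 12 of 60. With X ~ Binomial(60, p), P(X ≥ 12) = Σ C(60,k) p^k (1−p)^(60−k) for k = 12 to 60. The documents give no reaction rates, so p (the chance that a subject drops because of a drug adverse effect) is an assumed range:

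| p | P(at least 12 of 60) |
|---|---|
| 1% | 9 × 10⁻¹³ |
| 2% | 2 × 10⁻⁹ |
| 5% | 0.00004 |
| 10% | 0.015 |
| 15% | 0.18 |

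The rule applies at any point, so one early case, such as 1 of 5, can trip it. In 100,000 simulated trials with p = 1%, the line was crossed at some time in 5.0% when counting from the first subject, but in 0.5% when counting from the tenth. In addition, Section 8 keeps a subject who stops the drug in follow-up, so that subject may not count as dropped. This limb is not a reliable backstop for a rare reaction.

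**3. Enrolment during the delay (non-serious AEs only)**

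Inputs: 60 subjects (Précis; Section 3) and 2 years of enrolment (Section 3). Assumptions: even accrual, and annual summaries on the anniversaries of the start of enrolment.

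- Rate: 60 / 2 = 30 a year, or 30 / 52 = 0.58 a week.
- Event just after a summary: up to 30 × 1 = 30 further enrolees.
- Event at a random time in the year: 30 × 0.5 = 15 on average.
- For comparison, 5 business days: about 0.6 of a subject.

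Each subject takes only one of the two drugs, and the split is not given. If a fraction f takes the drug in question, the upper bound is 30f and the mean 15f: 7.5 and 3.75 for f = 0.25; 15 and 7.5 for f = 0.50; 22.5 and 11.25 for f = 0.75. Section 3 enrols until 60 subjects complete, so replacing dropouts would raise these figures somewhat.

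**The case against.** The strongest reply has four parts.

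- **Severe forms are already caught.** A life-threatening or hospitalized reaction is an SAE. This stands and limits the gap to events short of that.
- **Milder events are not ignored.** Staff and providers report all AEs and potential AEs to the principal investigator (Section 7.4). A subject who calls about side effects speaks to a study physician (Section 7). AEs are followed until resolved or stable (Section 7.5). Nothing forbids earlier contact with the monitor. This stands as clinical oversight, but it is not independent review, and the only route to the monitor that Section 7.3 prescribes for such events is the annual one.
- **Appendix G may supply definitions and time limits.** This cannot be excluded. Section 7.3 nevertheless states its own routes, so the two would have to agree.
- **Nothing in the protocol requires a medically-important-event limb.** This is correct. The limb is a recommendation and does not correct an arithmetical or logical error.

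A reader might also infer more than the text supports. One might read the *anticipated* wording as defeating Section 9.4; it does not, because that trigger has no expectedness condition. One might think that the monitor hears of anticipated SAEs only once a year; the annual interval there applies to NCCIH, and the monitor is told according to its own requirements. One might conclude that drug-related events are the likeliest to go slowly; the statement that no serious events are anticipated with amitriptyline could equally put them on the 5-day route.

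**Conclusion.** The point holds in two parts of unequal weight.

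The firmer part is the definition. A reaction named in Section 7 or 7.1 that involves no threat to life, admission or disability is a non-serious AE under Section 7.3. It misses the SAE limb of Section 9.4, probably misses the 20% limb, and is due to the monitor only in the annual summary. The enrolment figures above are an upper bound and a mean for this class alone. They rest on even accrual and cover both drugs together.

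The lesser part is an inconsistency. Sections 7.3 and 9.4 treat an anticipated, drug-related SAE differently, the key term is undefined, and neither section gives a time to the monitor. The monitor meeting is still required.

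Both parts are subject to Appendix G. The change is worth making because it is small and bears on the reactions for which the protocol wrote its own exclusions.

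**What to change.** Change the reporting text only; nothing here bears on dosing or on clinical management.

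1. In the Section 7.3 SAE definition, add a limb for a medically important event that, in the investigator's judgement, may need intervention to prevent one of the listed outcomes. Cite the reactions in Sections 7 and 7.1 as examples to be assessed. They should not be serious automatically, or every mild rash or change in heart rate would open a monitor meeting.
2. Reconcile Sections 7.3 and 9.4. Apply the existing 5-business-day report to the monitor and IRB to any SAE judged likely due to amitriptyline or omeprazole, anticipated or not, and state that this report opens the Section 9.4 meeting. Say that *intervention* in Section 7.3 includes the study drug. If *anticipated* is kept for other purposes, tie it to a named list and reconcile it with the Section 7 statement on amitriptyline.
3. Align Appendix G with the revised text. State also how Sections 8 and 9.4 fit together on whether a subject who stops the drug but stays in follow-up counts as dropped.

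The cost is a few sentences in the protocol, matching lines in the monitoring plan, and a few extra expedited reports.

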7.4 Reporting Procedures

Study staff and visit intervention providers will be instructed to report all adverse events (or potential AEs) to the study PI ([name]). Determination of relatedness will be made in conjunction with [name] and/or [name]. An electronic log of various types of AEs will be kept and updated by study staff.

7.5 Follow-up for Adverse Events

AEs will be followed-up by the study PI by phone calls to the subject and/or

monitoring of the medical record until they are resolved or considered stable. Formal AE follow-up will end with subjects' follow-up visit unless they have an ongoing issue or call to report an event after completing the study.

7.6 Safety Monitoring

Please see the separate data safety and monitoring plan for this study, found in Appendix G.

8. INTERVENTION DISCONTINUATION

Subjects who decline to participate in study procedures (e.g., completion of study questionnaires, physiologic monitoring, and/or video recording) will be terminated from the study without further follow-up. Any subjects who are disruptive or felt to pose a threat to study staff will also be terminated without follow-up. If a subject experiences an adverse reaction to amitriptyline or omeprazole and decides to stop taking the medication, or if a study physician deems it in the subject's best interest to stop the medication, the subject will continue to be followed for the duration of their initially planned participation (out to 8 weeks), unless the subject declines to participate further.

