5. STUDY INTERVENTIONS

5.1 Interventions, Administration, and Duration

Subjects will be randomized to receive either a “standard visit” or an “expanded visit” with a study provider. The standard visit is based on a high quality, empathic, conventional primary care encounter. The expanded visit is based on an integrative medicine consultation. Both visits are based on a script of questions and statements to the patient/subject (see Appendix E). The standard visit script includes questions about GERD history, symptoms, prior evaluation and treatments, and past medical history as well as a brief physical exam. The expanded visit script includes the same questions as the standard visit script plus additional questions that inquire about the modalities of their GI symptoms (e.g., nature of the reflux taste, sensation of heartburn pain and/or abdominal fullness, time of day better/worse), details about non-GI symptoms, quality of sleep, the effect of the weather on symptoms, food cravings and aversions, menstrual flow, fears/phobias, and overall temperament. In this way, the expanded visit tries to understand the patient’s/subject’s constitution in a way that many systems of integrative medicine attempt to do. To reduce the potential for introducing bias by using the words “standard” and “expanded”, the visit templates that the study providers will follow will simply refer to the number of questions to be asked on the template (e.g., 6 Question Template).

At the end of both the standard and expanded visits, the provider will recommend the subject take the study medication and describe how to take it and what to expect. Subjects will receive the same scripted advice in both groups. Each subject will receive an 8-week supply of amitriptyline or omeprazole with instructions for how to take it (10 mg daily at bedtime or 20 mg daily when waking up, respectively).

In our pilot study⁶⁴ we did not limit the amount of time spent with the study subject. On average, the standard visit lasted 18 minutes (range 11-32 minutes) and the expanded visit lasted 42 minutes (range 23-74 minutes). The study providers will be instructed to maintain equal empathy in both groups (e.g., kind and friendly manner, maintain eye contact, active listening and repeating back the patient’s words, expressions of empathy). Thus, the main differences between the visits will be the length of time spent with the subject and the additional questions that are asked.

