- Baseline Symptom Diary – 7-day diary indicating the frequency and severity of 9 different GERD and dyspepsia-related symptoms on a 5-point scale as well as any medications, supplements, or other products used to help manage symptoms. The first 3 symptoms (daytime heartburn, nighttime heartburn, and acid reflux) will be used to assess severity of GERD symptoms.
- GERD-HRQL – a validated 11 item scale for assessing the impact of GERD symptoms on health-related quality of life⁷³.
- NIH PROMIS GERD scale – a validated 13 item instrument assessing frequency and severity of GERD symptoms over a 7-day recall period²⁶.
- GSRS: The Gastrointestinal Symptom Rating Scale is a validated 15 item instrument for measuring the severity of gastrointestinal symptoms⁷⁴. It contains 5 subscales: abdominal pain, reflux syndrome, diarrhea syndrome, indigestion syndrome, and constipation syndrome.
- Current Stress Question – 1 item self-report measure of current stress level on a scale of 0 (no stress) to 10 (extreme stress)
- Perceived Stress Scale (PSS) – a widely used 10 item measure of perceived stress that has been shown to correlate with a variety of different health outcomes⁷⁵. We have adapted the originally validated measure to ask about stress over the past week (7 days), rather than the past month, to better fit the timeframe of the study. We have used this timeframe in other studies.
- NEO Five Factor Inventory (NEO-FFI) – a validated 60 item instrument that measured five major dimensions of personality: extraversion, neuroticism, agreeableness, conscientiousness, and openness to experience⁷⁶. Some dimensions have been associated with response to enhanced patient-provider interactions in others' studies⁷⁷.
- Physiologic Measures and Video Recording: During the intervention we will measure HRV, respiratory rate, skin temperature, and GSR in both study patients and study providers. The study visit will also be video recorded. During the COVID-19 pandemic, in order to allow us to collect physiologic and nonverbal behavior data (e.g., smiles) with the patient and physician unmasked, while also complying with institutional and state public health guidelines, the patient and doctor will sit in separate but adjacent, exam rooms with the door closed and use a video telehealth platform (e.g., Zoom, Cisco Meeting) to communicate. We will use the recording function to capture video data.

Evaluations for study providers:

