- Interpersonal Reactivity Index (IRI) – a validated 28 item self-assessment of cognitive and affective components of empathy⁷⁸.
- NEO Five Factor Inventory (NEO-FFI) – a validated 60 item instrument that measures five major dimensions of personality: extraversion, neuroticism, agreeableness, conscientiousness, and openness to experience [73]. Some dimensions have been associated with response to enhanced patient-provider interactions in others' studies⁷⁷.
- Demographics and practice – will assess things such as age, gender, race/ethnicity, and clinical experience (see Appendix D).
- Current Stress Question – 1 item self-report measure of current stress level on a scale of 0 (no stress) to 10 (extreme stress). Study providers will complete this question immediately prior to each study subject visit.
- Perceived Stress Scale (PSS) – a widely used 10 item measure of perceived stress that has been shown to correlate with a variety of different health outcomes⁷⁵. Study providers will complete this questionnaire immediately prior to each study subject visit.
- Fatigue Scale – 1 item self-report measure of the current fatigue level on a scale of 0 (no fatigue) to 10 (extreme fatigue). Study providers will complete this question immediately prior to each study subject visit.
- Physician Satisfaction Questionnaire (PSQ) – 20 item self-report measure assessing physician satisfaction with the patient visit. This measure includes a global satisfaction question and 19 items assessing 4 other domains: satisfaction with the patient-physician relationship, with the data collection process, with the appropriateness of the use of time, and with the absence of excessive demands on the part of the patient. Study providers will complete this questionnaire immediately after each study visit⁷⁹.

Randomization

Subjects will be randomized on the day of their baseline visit (Visit 1) to receive either the standard or expanded visit with the specific provider that they are scheduled to see that day. We will stratify randomization by provider so that each provider does the same proportion of standard and expanded visits. Randomization will occur during or immediately after subjects have completed their baseline questionnaires, immediately prior to the study visit.

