7. SAFETY ASSESSMENTS

Expected risks to subjects are as follows:

- Study questionnaires: Symptom and behavioral data collection involves virtually no risk; however, psychosocial tests or questions about symptom intensity may cause minor emotional distress. Because participants are free to stop at any time and will be reminded of this throughout the assessment process, the risk of distress is low. In our experience, such questionnaires are well-tolerated and complications are extremely rare.
- Discomfort from ECG/GSR leads and physiologic monitoring: Some participants may experience minor skin irritation due to the adhesive used to apply leads for physiologic monitoring. Subjects with known adhesive allergies will not be eligible to participate in the study. Some participants may experience psychological distress knowing that their physiology is being monitored. The physiologic monitoring will be described in the consent document and care will be taken to minimize such distress. Participants will be free to stop at any time. In general, such monitoring is well-tolerated.
- Discomfort from blood draws: some participants may have an aversion to needles, blood, and/or the drawing of blood. Blood will be drawn by trained study staff or phlebotomists and care will be taken to minimize discomfort to participants. Blood draws are generally well-tolerated, although occasionally there may be bruising or discomfort at the site. Rarely an infection can occur. The blood draw will be an optional component of the study, and if an enrolled subject consents to the blood draw and is particularly challenging to draw blood from, we cancel the blood draw and will not require a successful blood draw to be a condition of continued enrollment in the study.
- Videotaping: Some participants may experience psychological distress knowing that they are being videotaped. Participants will be free to stop at any time. In general, videotaping is generally well-tolerated.

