9.3 Definition of Populations

For analyses including the intervention group type, we will analyze our data according to which visit intervention subjects received (standard or expanded). We do not anticipate any discrepancies between what subjects were assigned to receive by randomization and what they actually received. Study visit type will be guided by a written script that the providers will follow during the visit. The actual intervention received will also be verified by reviewing study video recordings.

The intent to treat analysis will include all randomized subjects who received a study visit intervention. The per protocol analysis will include all individuals who received a study visit intervention and completed the follow-up questionnaires at 8

weeks.

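### Section 8 ends all follow-up for a subject who declines recording or a questionnaire, with no limit to refusals before randomisation, so it can discard a week-8 diary outcome that could have been observed

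*Combined protocol and SAP*

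**What the plan says.** Section 8 covers subjects who decline study procedures, giving questionnaires, monitoring and video as examples. They, in the case of "physiologic monitoring, and/or video recording) will be terminated from the study without further follow-up", leave the trial entirely. The same section treats a subject who stops the study drug differently: "the subject will continue to be followed for the duration of their initially planned participation", unless the subject declines. Section 7 adds that an unsuccessful optional blood draw does not affect continued enrolment.

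On timing, Section 6.2.3 states: "Randomization will occur during or immediately after subjects have completed their baseline questionnaires, immediately prior to the study visit". It also states: "During the intervention we will measure HRV, respiratory rate, skin temperature, and GSR in both study patients and study providers". The video is taken at the same visit, and Section 6.2.5 places the rapport and empathy questionnaires straight after it. On monitoring, Section 7 says: "Participants will be free to stop at any time. In general, such monitoring is well-tolerated". It gives the same freedom for video and questionnaires.

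The primary outcome (Sections 9.1 and 9.5.1) uses three diary items averaged over seven days, at baseline and in the last week. Section 5.4 says that where diary data are insufficient, symptoms are taken as unchanged from baseline. Section 9.3 says: "The intent to treat analysis will include all randomized subjects who received a study visit intervention". The per-protocol set also requires the 8-week questionnaires. Section 3 continues enrolment until 60 subjects complete. Section 9.2 gives no dropout rate.

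**The concern.** The recorded procedures and post-visit questionnaires serve the secondary aims. A subject can receive the randomised visit, take the sensors off or refuse a form, and still be willing to keep a diary. As written, Section 8 gives that diary up. It also ends the scheduled adverse-event questions and the debriefing, both of which take place at Visit 2. The subject may by then hold study medication, because Section 5.2 has it handed over at the end of Visit 1.

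Stopping during or after the visit is an event after randomisation, and the visit is the randomised intervention. If stopping depends on the length or content of the visit, the missing outcomes are not a random subset, and the two arms may lose different numbers and kinds of subjects. The plan offers a fixed imputation or exclusion in place of data it could have had. With 30 per arm and no dropout allowance, each avoidable loss counts.

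**Working it through.** **Passages side by side.**

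| Event | Consequence in the plan |
|---|---|
| Stops study drug (Section 8) | Followed to 8 weeks |
| Optional blood draw fails (Section 7) | Stays enrolled |
| Declines monitoring, video or questionnaire (Section 8) | Terminated, no follow-up |

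Willingness to be recorded is an entry criterion (Section 4.1). It is checked before randomisation, so it makes a later refusal less likely but does not rule one out. Enrolling to 60 completers replaces numbers but does not remove selection.

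**1. The plan's own figure.** Inputs from Section 9.2: 30 per arm, 80% power, two-sided alpha 0.05, SD 1.5 / 2.0 / 2.5. The normal approximation for SD 1.5 is (1.960 + 0.842) × 1.5 × √(2/30) = 1.085. A two-sample t-test (noncentral t, 58 df) gives 1.103 / 1.471 / 1.839. This matches the stated 1.10 / 1.47 / 1.84.

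**2. Exposure ratio.** From the pilot means in Section 5.1: 42/18 = 2.33. From the pilot ranges: minima 23/11 = 2.09, maxima 74/32 = 2.31. This trial sets no visit length, but Section 5.1 keeps length as a main difference between the visits.

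**3. Assumed stopping rates.** The documents give none. Assume that 5-10% of the expanded arm stop and that stopping is proportional to recorded time:
- Expanded: 0.05 to 0.10, or 1.5 to 3 of 30.
- Standard: 0.05 × 18/42 = 0.021 to 0.10 × 18/42 = 0.043, or about 0.6 to 1.3 of 30.

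**4. Completer comparison.** Let stoppers improve δ points less than others in their arm, with δ assumed to be 1 to 2. Then bias = (p_E − p_S) × δ:
- (0.05 − 0.021) × 1 = 0.03
- (0.10 − 0.043) × 2 = 0.11

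The upper value is 0.11/1.10, about 10% of the minimal detectable difference. Under these assumptions it favours the expanded arm.

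**5. Unchanged-from-baseline rule.** Let m_E and m_S be the improvement the stoppers would have shown. Setting it to zero gives bias = −(p_E × m_E − p_S × m_S). Assume a true difference of 1.10, a standard-arm improvement of 0.5 to 1.5, and stoppers who would have improved like the rest of their arm (m_E = 1.6 to 2.6):
- 5% stopping: 0.05 × 1.6 − 0.021 × 0.5 = 0.07; 0.05 × 2.6 − 0.021 × 1.5 = 0.10
- 10% stopping: 0.10 × 1.6 − 0.043 × 0.5 = 0.14; 0.10 × 2.6 − 0.043 × 1.5 = 0.20

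The expected difference falls from 1.10 to between 1.03 and 0.90. If the stoppers would not have improved at all, the imputed value is correct and this bias is zero. If the standard arm lost more improvement, the sign would reverse.

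**6. With the fix.** If every such subject stays in diary follow-up, loss by this route is zero in both arms and the Section 9.2 calculation is unaffected by it.

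**The case against.** The strongest reply has four parts.

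First, Section 8 speaks of declining, not of stopping partway, and does not mention randomised subjects. It could be meant for outright refusal at the start. That reading is possible, but nothing in the text limits the rule to it. The freedom in Section 7 ("Participants will be free to stop at any time") makes refusal during the visit foreseeable. If only early refusal was meant, the same edit would say so.

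Second, few subjects may stop. All have agreed to recording before randomisation, and the plan describes monitoring and video as generally well tolerated. This stands, and it lowers the priority.

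Third, a reader might infer that the expanded arm will lose primary data about 2.3 times as often. The documents do not support that. The ratio is a pilot average, and no stopping rate is given. Discomfort might arise when sensors are attached, before the visits diverge. Sections 2.1 and 2.2 suggest that empathic or integrative visits may relax patients, which could reverse the direction. The questionnaires are the same in both arms, so recording time says nothing about them.

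Fourth, a reader might infer that these procedures alone cost a subject the primary outcome. They do not: Section 8 also terminates disruptive or threatening subjects, and Section 7 allows possible removal for severe GERD symptoms.

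Requiring recorded procedures is also understandable in a mechanism study. That supports the entry criterion. It does not justify giving up the diary of a subject already randomised and seen.

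**Conclusion.** The point holds as an avoidable loss of observable primary outcomes. It rests on the text alone: the termination rule, the timing of recording and post-visit questionnaires after randomisation, the freedom to stop, and a primary outcome that needs only the diary. Nothing elsewhere in the plan recovers the data.

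Two matters are unclear. Section 9.3 does not say whether an interrupted visit counts as received, and so whether the subject enters the intent-to-treat set. Section 5.4 is written around incomplete returned diaries; it is the plan's only rule for a missing primary outcome, and the calculation above assumes that it also covers a terminated subject.

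Differential loss by arm is a possibility, not a finding. On assumed stopping of 5-10% in the expanded arm, proportional to recorded time, the completer bias is about 0.03 to 0.11 points. Under the unchanged-from-baseline rule the shift is about 0.07 to 0.20 points the other way, if stoppers would have improved like the rest of their arm. Both ranges depend on rates the documents do not give. The likely number of subjects is small. Priority is low to moderate, and the case for acting is that the change is cheap.

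**What to change.** In Section 8, state that a randomised subject whose study visit has begun and who then declines monitoring, video or a questionnaire stops that procedure only. Diaries, check-in calls and Visit 2, including adverse-event questions and debriefing, continue unless the subject withdraws consent. State in Section 9.3 that such a subject stays in the intent-to-treat set under the assigned visit type, even if the visit was interrupted. Report by arm how many stopped each procedure. Keep willingness to be recorded as an entry criterion, and leave the rule on threatening behaviour as it is.

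The cost is a short amendment to Sections 8 and 9.3 with matching consent wording, and no new procedures. The downside is that a few subjects will have primary data but incomplete physiology or video. For them the video check of the visit delivered (Section 9.3) and the fidelity review (Section 5.1) will also be missing or partial.
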